### ***Statistical analysis***

#### *Descriptive analysis*

Descriptive statistical methods (percentage and numbers on total) will be used to analyze the evaluated parameter

#### *Inferential analysis*

Data will be calculated at patient level and implant/tooth level. VAS score will be considered as the main outcome (quantitative).

If the distribution is normal, the following tests will be used:

- Binary categorical variables: T-Student / Fisher's exact test;
- Categorical variables with > 2 categories: ANOVA;
- Quantitative variables: Simple linear regression / Pearson correlation coefficient.

If it doesn't follow normality:

- Binary categorical variables: U of Mann-Whitney;
- Categorical variables > 2 categories: H of Kruskal-Wallis;
- Quantitative variables: Spearman's correlation coefficient.

[figure not shown]

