#### b) Specific Hypothesis

1. SPT with conventional ultrasonic device will result in more pain/discomfort around dental implants than in teeth.
2. SPT by means of an erythritol based air-polishing powder (Air Flow Master®, Air-Flow Plus®, EMS, Nyon, Switzerland) will result in better patient reported outcomes and same clinical outcomes, at the first SPT and after 2 years.
3. SPT by means of an erythritol based air-polishing powder (Air Flow Master®, Air-Flow Plus®, EMS, Nyon, Switzerland) will result in the increase of the compliance rates after 2 year of follow-up.

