### ***Subject Selection***

The study will be performed after the approval of the Ethics Committee of the Universitat Internacional de Catalunya (UIC) and will be conducted according to the principles outlined in the Declaration of Helsinki and Ethical Conduct for Research with Human Beings.

An aleatoric list of patients who have been enrolled in SPT at the Department of Periodontology of UIC and met the inclusion criteria will be generated – those patients will be called for SPT visit by the same investigator ([name])

Criteria for subject selection will be as follows:

- (1) Patients aged 18 to 80 years who are healthy;
- (2) Partially edentulous patients, rehabilitated with at least one dental implant in the maxilla or mandible;
- (3) No implant mobility;
- (4) Treated periodontal disease;
- (5) No systemic diseases that could influence the outcome of the therapy (i.e. uncontrolled diabetes, osteoporosis, bisphosphonate medication).
- (6) Non-smoker or light smoking status in smokers (<10 cigarettes/day).

Pregnant, lactating women and non-collaborating patients will be excluded from the study.

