### **Randomization and study groups**

Once oral hygiene instructions were provided, patients will be randomly assigned to the Test or Control groups. Allocation of patients will be decided following randomization tables with permuted blocks of four while the information will be concealed by using opaque envelopes, which will be labelled with the patient study number and only be revealed after oral hygiene instructions are provided.

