## **SPECIFIC COMMISSION OF THE DOCTORAND**

years of follow-up. Additionally, a periapical radiograph of all implants involved in the study will be taken at 1 year and 2 years of follow-up. Individual compliance will be registered as well in the CRF.

Patients will be further motivated with respect to oral hygiene habits during the entire period of the study.

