#### **Secondary outcome;**

- *Changes in the following clinical variables: FMPI, FMBI, PPD, GR, mPI, mBI, SOP, Implants PPD and MR after decontamination during SPT.*
- Compliance to SPT reported after decontamination during SPT.

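### Tooth- and implant-level tests have no stated allowance for clustering within patients and no rule on which level decides, and no paired test is named for the implant-versus-tooth pain comparison

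*Combined protocol and SAP*

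**What the plan says.** **Level of analysis and tests.** Inferential analysis: "Data will be calculated at patient level and implant/tooth level". VAS is then named as the main, quantitative outcome. For normal data the two-group entry begins "Binary categorical variables: T-Student" and adds Fisher's exact test. For non-normal data it is "Binary categorical variables: U of Mann-Whitney". The other entries are ANOVA, simple linear regression with Pearson correlation, Kruskal-Wallis and Spearman. A figure after the list is not reproduced in the public text.

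**Unit of randomisation.** Randomization and study groups: "Allocation of patients will be decided following randomization tables with permuted blocks of four".

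**Units per patient.** Subject Selection, criterion 2: "Partially edentulous patients, rehabilitated with at least one dental implant in the maxilla or mandible". No maximum is set and no index implant is chosen. Clinical Parameters takes probing depth, recession and the implant plaque index at six sites per tooth or implant.

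**Outcomes exposed.** Secondary outcome: "Changes in the following clinical variables: FMPI, FMBI, PPD, GR, mPI, mBI, SOP, Implants PPD and MR". Specific Hypothesis 2 expects that the test treatment "will result in better patient reported outcomes and same clinical outcomes".

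**Implant versus tooth pain.** Specific Hypothesis 1 predicts more pain around implants than teeth under the conventional ultrasonic device. The VAS section takes one score after the teeth and another after the implants, from the same patient.

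**The concern.** Teeth and implants in one mouth share hygiene, smoking, host response and operator, so their measurements will usually be positively correlated. A test that counts each tooth or implant as an independent observation then understates the standard error of the arm difference. No section names a mixed model, generalised estimating equations (GEE), a cluster-robust error or a rule for summarising to the patient.

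For hypothesis 2, unit-level testing could produce spurious arm differences and wrongly contradict the prediction of equal clinical outcomes. With two levels planned and no hierarchy, nothing says which result counts when they disagree.

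The pairing gap is a separate matter. Hypothesis 1 uses the main outcome variable, probably in about 15 control patients. Student's t is named without saying paired or independent, and the only non-normal two-group option is an independent-samples test. A real difference could be missed.

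**Working it through.** **1. The plan's own sample size.** Inputs from Sample Size Calculation: difference 1 mm in clinical attachment level (CAL), SD 0.9, alpha 0.05 (two-sided assumed), power 80%, loss 12%.

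n per arm = 2 × (1.96 + 0.84)² × 0.9² / 1² = 12.7, so 13. Then 13 / 0.88 = 14.8, so 15 per arm and 30 in total.

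The stated 30 is reproduced. It counts patients and contains no design effect.

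**2. Clustering, t-test and Mann-Whitney.** With m units per patient and intraclass correlation ICC, the design effect is DE = 1 + (m − 1) × ICC. The true type I error of a unit-level test at nominal 5% is 2 × [1 − Φ(1.96/√DE)]. The documents give neither m nor ICC, and the outcomes are changes, so both are assumed. The last two columns are simulations with 15 patients per arm.

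| Units per patient | ICC | DE | Formula | t-test | Mann-Whitney |
|---|---|---|---|---|---|
| 1 | any | 1.0 | 5.0% | 5.3% | 4.7% |
| 2 | 0.1 | 1.1 | 6.2% | 6.2% | 5.8% |
| 2 | 0.5 | 1.5 | 11.0% | 11.3% | 10.6% |
| 3 | 0.1 | 1.2 | 7.4% | 7.2% | 7.3% |
| 3 | 0.5 | 2.0 | 16.6% | 17.1% | 17.0% |
| 10 | 0.1 | 1.9 | 15.5% | 15.1% | 14.6% |
| 10 | 0.3 | 3.7 | 30.8% | 31.3% | 30.3% |
| 20 | 0.1 | 2.9 | 25.0% | 24.4% | 23.6% |
| 20 | 0.3 | 6.7 | 44.9% | 45.0% | 44.5% |

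A t-test on patient means stayed at 4.8% to 5.3% in all these settings.

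**3. Clustering, Fisher's exact test.** Fisher's test is conservative in small samples, which offsets some of the inflation. Simulated type I error with 20% / 40% of implants positive:

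- 2 implants: 3.1% / 3.5% at ICC 0.1; 6.3% / 7.4% at ICC 0.5.
- 3 implants: 4.2% / 4.6% at ICC 0.1; 12.2% / 12.7% at ICC 0.5.

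So for binary bleeding or suppuration the error exceeds 5% only at higher correlation or with more units per patient.

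**4. Pairing for hypothesis 1.** n = 15. The difference is in units of the SD of a single score, and r is the tooth-implant VAS correlation; both are assumed. The SD of the within-patient difference is √[2(1 − r)]: 1.18, 1.00 and 0.77 at r = 0.3, 0.5 and 0.7. The paired test uses this smaller SD; the unpaired test uses √2 = 1.41 whatever r is.

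| r | Type I error, unpaired t | Power at 0.7 SD: unpaired / paired | Power at 0.5 SD: unpaired / paired |
|---|---|---|---|
| 0.3 | 2.1% | 45% / 57% | 23% / 33% |
| 0.5 | 0.8% | 44% / 71% | 20% / 44% |
| 0.7 | 0.1% | 44% / 90% | 16% / 64% |

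The rank tests behave alike at 0.7 SD: Mann-Whitney 39% to 41%, Wilcoxon signed-rank 54% to 89%. At r = 0 pairing gains nothing (45% unpaired, 43% paired).

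**The case against.** **The list may be for VAS only.** It follows directly after the sentence naming VAS, and it can be read as tests of one quantitative outcome by type of explanatory variable. The implant/tooth level could then mean the two VAS readings. This is a fair reading, and the clustering consequence depends on it. Against it, Fisher's exact test cannot be applied to a quantitative VAS, so the list appears to reach binary outcomes. If it does not, the tooth- and implant-level secondary outcomes have no stated test, which is also a gap. The pairing point stands either way, because it concerns VAS.

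**Patient-level analysis is planned too.** True, and it is valid. What is missing is a statement that it decides.

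**The consequences are bounded.** This stands. Clustering touches secondary outcomes only, and spurious differences would work against hypothesis 2, not for an efficacy claim. The unpaired test creates no extra false positives under positive correlation. Student's t does not exclude the paired form, so the firm omission is in the non-normal branch. Pairing is no cure for a small sample: at 0.5 SD even the paired test has only 33% to 64% power.

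**The number of implants is unknown.** This also stands. The follow-up text says "a periapical radiograph of all implants involved in the study will be taken at 1 year" and again at 2 years. A reader might infer that every implant a patient has enters the analysis, but the sentence covers radiographs of study implants, and no radiographic outcome is listed. CAL should not be counted among the exposed outcomes: it is sized per patient and is absent from the outcome lists.

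**Conclusion.** The concern holds as an omission with a known direction. If the listed tests are used on teeth or implants for tooth probing depth (PPD), recession (GR), implant plaque (mPI) and bleeding (mBI) indices, suppuration (SOP), implant PPD and mucosal recession (MR), t-test and Mann-Whitney p-values are too small under positive within-patient correlation. Fisher's test is inflated only at higher correlation or with more units per patient. For hypothesis 1, an unpaired test loses power under positive correlation.

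The sizes above are illustrations. ICC, units per patient, VAS correlation and effect size are all assumptions, and the figure after the test list could not be checked.

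Two stronger conclusions might be inferred and are not supported:

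- That the main comparison is compromised. Each patient gives one tooth and one implant score per session, so between-arm VAS is unaffected provided the two are not pooled as independent. Compliance, the full-mouth plaque and bleeding percentages (FMPI, FMBI) and all patient-level analyses are also unaffected.
- That all p-values under the plan are too small. The Fisher results at ICC 0.1 and the unpaired VAS test both err in the conservative direction.

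This should be fixed before analysis, but it does not undermine the trial's main result.

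**What to change.** In Inferential analysis:

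1. State that the patient-level analysis is decisive. Define one summary per patient for each clinical outcome: the mean over sites, or the proportion of bleeding or suppurating sites for mBI and SOP.
2. For any tooth- or implant-level analysis, account for clustering by patient, with a mixed model with a random patient intercept or GEE with a small-sample correction. Label it supportive. If the model does not converge, report the patient-level result only.
3. Test hypothesis 1 on each patient's implant-minus-tooth VAS, with a paired t-test or the Wilcoxon signed-rank test.
4. State which outcomes the test list covers, and that tooth and implant VAS are not pooled as independent observations in the between-arm comparison.

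The cost is a few sentences and slightly more analysis work, with no extra patients, visits or data. Unit-level results will look less precise than the listed tests would suggest. If the two VAS scores turn out uncorrelated, pairing costs about 1 to 4 points of power.

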- Wennstrom JL, Dahl\_en G, Ramberg P. Subgingival debridement of periodontal pockets by air polishing in comparison with ultrasonic instrumentation during maintenance therapy. *J Clin Periodontol* 2011; 38: 820–827.

b. Diagrama de flujo que cuente con una línea de tiempo de los sujetos del estudio (acorde a los grupos estudiados)

- To evaluate pain/discomfort during SPT around dental implants and teeth.
- To evaluate patient reported outcomes and clinical variables by decontamination during SPT with erythritol based air polishing powder (Air Flow Master®, Air-Flow Plus®, EMS, Nyon, Switzerland), at the first SPT and after 2 years.
- To evaluate the effect of erythritol based air polishing powder (Air Flow Master®, Air-Flow Plus®, EMS, Nyon, Switzerland) during SPT on the compliance rates after 1 and 2 years of follow-up.

Investigador/a Principal

Fdo: Dr./Dra.
